Title: Pragmatic Cyclical Lower Extremity Exercise Trial for Parkinson's disease

NCT #: NCT04000360

Document Date: November 9, 2021

Title: Pragmatic Cyclical Lower Extremity Exercise for Parkinson's Trial

PI: [name]

Date Modified: 11/9/2021

SPECIFIC AIMS

An unmet need in the treatment of Parkinson's Disease (PD) is identification of an effective disease-modifying intervention (e.g. pharmaceutical, surgical or behavioral).^{1,2} Increasing evidence, from our laboratory³⁻⁷ and others,⁸⁻¹⁰ coupled with our recently completed NIH-sponsored randomized controlled trial (RCT), *CYClical Lower Extremity exercise for Parkinson's trial (CYCLE)*, indicates high intensity aerobic exercise is a candidate to alter PD progression. CYCLE trial data demonstrate that exercise delivered in a controlled, supervised laboratory setting results in global improvements in motor and non-motor function. Global improvements were preserved following exercise cessation, suggesting exercise is likely enhancing CNS function.^{3,4,7} The precise mechanism underlying improved post-exercise motor function in PD is unknown. Our imaging data^{5,6,11} and others^{12,13} suggest a plausible mechanism is improved thalamo-cortical connectivity, facilitated through elevation of neurotrophic factors.^{14,15} A multi-site pragmatic RCT is proposed, in which PD patients complete the CYCLE protocol at home, to address the following questions: 1) What are the disease-altering capabilities of a PD-specific long-term, high intensity aerobic exercise intervention? 2) What are the relationships of patients' phenotype and exercise performance variables to PD progression within such an exercise program? Based on preliminary data, we hypothesize that long-term high-intensity aerobic exercise slows PD progression relative to Usual and Customary Care (UCC). In sum, approximately 250 mild to moderate PD patients from Cleveland Clinic and University of Utah will be randomized to a high-intensity home exercise or a UCC group. The CYCLE protocol, involving aerobic intensity between 60-80% of heart rate reserve with a target cadence between 80-90 RPMs, will be delivered to the patients' home via the commercially available *Peloton Cycle*. The exercise group will be asked to cycle 3x/week for 12 months. The UCC group will be instructed to engage in their normal activities. The Movement Disorder Society Unified Parkinson's Disease Rating Scale (MDS-UPDRS III) will be used to evaluate disease progression or rate of physical decline. Blinded MDS-UPDRS III evaluations will be completed at: enrollment, 6 and 12 months. Biomechanical iPad assessments of motor and non-motor function¹⁶⁻¹⁹ will be completed at each time point; thus augmenting clinical outcomes to provide a comprehensive understanding of the effects extended exercise on specific aspects of PD motor control and executive function. Overall activity levels will be monitored for both groups via a wearable sensor.

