Title: Pragmatic Cyclical Lower Extremity Exercise Trial for
Parkinson's Disease

NCT#: NCT04000360

Document Date: January 29, 2024

The Cyclical Lower Extremity Exercise for Parkinson Disease II (CYCLE-II) Study
Principle Investigator: [name].
Site Principal Investigator: [name].

Statistical Analysis Plan: Assessment of Treatment Effect
Study Statistician: [name].

Overview

CYCLE-II is a pragmatic two center, blinded examiner, 1:1 randomized clinical trial to assess whether one year of a home Peloton-cycle based aerobic exercise regimen alters Parkinson's disease progression from that of patients receiving usual care and usual physical activity. The trial is conducted at the Cleveland Clinic and the University of Utah, coordinated by the former. The CYCLE-II study design and basic analytic plan have been published (*Phys Ther* 2021 Nov; 101(11):pzab191, PMCID: PMC8632855). Multiple prespecified quantitative outcomes are hierarchically classified as primary inferential, secondary inferential, and descriptive exploratory outcomes, and assessed in randomly ordered on and off Parkinson's medication examinations at baseline, and again off medication at six and 12 months. Parkinson's disease progression is to be assessed in each group by the estimated annual rates of change of off-medication outcome measures, and the treatment groups are to be compared in intention-to-treat analyses of these estimates.

Study Outcomes

The primary outcome is the total score on the Movement Disorder Society Unified Parkinson's Disease Rating Scale Part III: Motor Examination, an assessment of the motor signs of Parkinson's disease by an examiner masked to the participant's treatment group. Secondary inferential motor outcomes are:

- i. Upper extremity dexterity: time to complete a iPad-based modification of the Nine Hole Peg Test;
- ii. Lower extremity functional mobility
 - a. time to complete an iPad-instrumented Time Up and Go Test;
 - b. average turn velocity on an iPad-instrumented Time Up and Go Test;
- iii. Ambulation gait speed
 - a. average "comfortable speed" velocity on the Ten Minute Walk Test;
 - b. average "fast speed" velocity on the Ten Minute Walk Test;

Secondary non-motor outcomes are:

- i. Neural processing speed: number correct on the New Processing Speed Test;
- ii. Episodic visual memory: Number of locations + number of symbols correctly recalled on the New Symbol Modalities Test;

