The distributions of baseline variables will be summarized, overall and by treatment group, by frequency distribution for dichotomous and other categorical factors, mean and standard deviation for reasonably symmetrically distributed quantitative variables, and Tukey five-number summaries (median, quartiles, extrema) for substantially skewed variables. We will also examine boxplots, histograms and kernel density estimators for continuous variables, and use standardized mean differences for continuous variables and categories of nominal and ordinal variables to describe balance of the randomized treatment groups.

Outcome description and distributional assessment

All prespecified outcomes are quantitative or potentially treatable as such depending on the degree to which their full scales occur in our study population. We will thus describe each initially as indicated above for quantitative baseline variables, overall and by treatment \times time combinations, including visually using grouped boxplots and kernel density estimators. To assess compatibility with the assumptions of the planned analytic approach, for each outcome we will use restricted (equivalently, residual) maximum likelihood (REML) estimation to fit preliminary mixed models with fixed effects of randomized treatment, visit, and their interactions, and with unrestricted covariance matrices -- thus allowing within treatment and visit variability to change over time and accounting for arbitrary correlations between measurements of the outcome in the same patient at different visits. These models will not be used to estimate treatment effects, but only to assess the compatibility of their residuals with the requisite distributional assumptions about random noise to support validity of fixed effect estimates and tests from the planned inferential analyses.

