Estimated skewness, excess kurtosis, quantile-quantile (qq) plots, boxplots, and residual vs. predicted (for the six treatment \times time combinations) plots, particularly of Studentized and standardized residuals, will be used for this purpose. We will not use formal hypothesis tests of normality of the residual distributions, as the relevant issue is not whether the data literally arise from a normal distribution, which is virtually never the case, but rather whether the extent of departure from normality is enough to meaningfully distort effect estimates and associated hypothesis tests. Models based on Gaussian assumptions are robust to modest to moderate violations of assumptions, particularly to the distributional assumption when samples are reasonably large, in which case formal tests of normality may have power against small and often inconsequential departures from it.

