For outcomes with distributional characteristics reasonably compatible with standard linear mixed model assumptions, we will employ prespecified linear mixed model analyses for the observations at baseline, six months, and twelve months, i.e., one year, as described below. For outcomes whose distributions, conditional on treatment and time, are substantially skewed and/or lighter or heavier tailed than Gaussian distributions (leptokurtotic or platykurtotic), we will consider applying the planned analysis to a Box-Cox and other reasonably straightforward data transformation of the outcome and backtransforming the results, and/or use of a generalized linear mixed model with log or other link function and/or a non-Gaussian exponential family or a beta error distribution. In exploring Box-Cox transformations, we will be generally guided by the independence pseudologlikelihood of the fitted fixed effects model saturated for treatment \times visit with clinical site as an additive covariate, as a function of the Box-Cox transformation power parameter. If and when transformations are used, we will report modeling results on the transformed scale and also report additive treatment effects, which for nonlinear transformations will vary by baseline value of the outcome, for selected percentiles of such baseline values. Nonparametric approaches such as quantile regression or product multinomial-based mixed categorical data models for marginal means will be considered as needed for bounded integer-scored outcomes with limited ranges and/or floor or ceiling effects, which may not admit of straightforwardly interpretable and communicable normalizing transformations.

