To control the overall false positive rate of claiming disease-modifying therapeutic benefit from the home Peloton-based aerobic exercise program at 5% in the context of CYCLE II's nine inferential and other descriptive/exploratory outcomes, interpretation of significance testing will be in accordance with a prespecified outcome hierarchy. Specifically,

- i. overall benefit will only be claimed if the test of the primary UPDRS III outcome is statistically significant in the direction of exercise superiority at a two-sided $\alpha=5\%$,
- ii. benefit will only be claimed for a secondary motor inferential outcome if i) is satisfied and if the treatment effect is also statistically significant for that secondary motor outcome after Holm-Bonferroni adjustment for multiple testing of the five secondary motor outcomes; and
- iii. benefit will only be claimed for a secondary non-motor inferential outcome if i) is satisfied and if the treatment effect is also statistically significant for that secondary non-motor outcome after Holm-Bonferroni adjustment for multiple testing of the three secondary non-motor outcomes;
- iv. benefit will not be claimed to have been demonstrated based on estimated treatment effects on any variable other than the nine prespecified primary and secondary endpoints, and any associated p-values and confidence intervals for such other variables will be presented as descriptive only and potentially for guidance by designers of subsequent studies, and specifically noted to be unadjusted for multiple comparisons of over a dozen outcomes.

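### The default mixed model can be replaced by judgement after unmasked by-arm displays, with no numeric trigger or lock, so control at 5% is not guaranteed

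*SAP*

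**What the plan says.** The steps are in the SAP, mainly under Outcome description and distributional assessment, in this order.

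1. Every prespecified outcome is first described overall and by treatment-by-time combination, "including visually using grouped boxplots and kernel density estimators".
2. A preliminary mixed model saturated for treatment and visit is fitted to each outcome. Its residuals are judged by skewness, kurtosis and several plots, among them "residual vs. predicted (for the six treatment"-by-time cells). Formal normality tests are ruled out, and no cut-off for skewness or kurtosis is given. The SAP says that these models serve only to check residuals and not to estimate treatment effects.
3. Outcomes judged reasonably compatible get the default: "prespecified linear mixed model analyses for the observations at baseline, six months, and twelve months". For substantially skewed or non-Gaussian-tailed outcomes, "we will consider applying the planned analysis to a Box-Cox and other reasonably straightforward data transformation of the outcome", or a generalized linear mixed model. Quantile regression or multinomial models may be considered for bounded integer scores with a limited range or floor or ceiling effects. A likelihood serves as a general guide to the Box-Cox power.
4. The covariance structure is then selected by BIC. Effects are estimated last, under Treatment effect estimation and testing.

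That last section states the aim "To control the overall false positive rate of claiming disease-modifying therapeutic benefit from the home Peloton-based aerobic exercise program at 5" per cent, and says that "overall benefit will only be claimed if the test of the primary UPDRS III outcome is statistically significant in the direction of exercise superiority". All secondary claims depend on that primary test. The only masking described in the SAP is that of the examiner (Overview; Study Outcomes).

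**The concern.** The six arm-by-visit summaries of MDS-UPDRS III largely show the treatment result. The person who sees them then decides whether the default stands, and the terms that govern the decision are qualitative. The primary outcome is not exempt.

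If a departure from the default is made, nobody can later verify that the residuals prompted it and not the arm difference. Because the primary test gates every secondary claim, any looseness there reaches all nine inferential outcomes. The exposure is also avoidable, since the shape of residuals can be judged without knowing which arm did better.

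**Working it through.** **Inputs from the documents.** Two-sided 5% with benefit claimed in one direction only (SAP, Treatment effect estimation and testing); "approximately 250 mild to moderate PD patients from Cleveland Clinic and University of Utah will be randomized" (Protocol, Specific Aims); "1:1 randomized clinical trial" (SAP, Overview), hence 250/2 = 125 per arm; visits at 0, 6 and 12 months.

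**Assumptions.** The documents give no SD, outcome shape, correlation or dropout. Assumed shapes were near-Gaussian (mean 36, SD 11), gamma (shape 6) and lognormal (log-SD 0.5). Data were complete, with AR(1) correlation of 0.6 or 0.8 between adjacent visits.

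**Step 1: the plan's own figure.** For one analysis fixed in advance, 2 × (1 − Φ(1.96)) = 0.050, of which 0.025 lies in the superiority direction. The stated 5% reproduces.

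**Step 2: the estimate.** With visits at t = 0, 0.5 and 1 year, the least-squares slope is (−0.5·y0 + 0.5·y12)/0.5 = y12 − y0. Each test compares this change between arms.

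**Step 3: null simulation.** Three ways of choosing the analysis were applied to the same data sets:
- *Residual rule:* stay on the raw scale unless the skewness of residuals centred within the six cells exceeds 0.5 (an assumed trigger). Otherwise take the best of identity, square root and log by the Box-Cox profile.
- *Ceiling, three scales:* count a rejection if any of identity, square root or log is significant.
- *Ceiling, five options:* as above, adding a log-link mean model and a median comparison.

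| Shape | Adjacent correlation | Raw scale fixed | Residual rule | Best of three | Best of five |
|---|---|---|---|---|---|
| Near-Gaussian | 0.6 | 0.0478 | 0.0478 | 0.0630 | 0.0835 |
| Near-Gaussian | 0.8 | 0.0499 | 0.0499 | 0.0703 | 0.0918 |
| Gamma | 0.6 | 0.0480 | 0.0486 | 0.0626 | 0.0778 |
| Gamma | 0.8 | 0.0500 | 0.0506 | 0.0690 | 0.0812 |
| Lognormal | 0.6 | 0.0530 | 0.0512 | 0.0699 | 0.0832 |
| Lognormal | 0.8 | 0.0486 | 0.0523 | 0.0705 | 0.0818 |

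There were 5,000 replicates for gamma and 10,000 for the others. The Monte Carlo standard error, √(0.05 × 0.95/N), is 0.0031 or 0.0022. The median test alone rejected in 2.6% to 4.0% of replicates, so the five-option ceiling is slightly low.

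**Step 4: a separate simulation.** This used skewed scores with mean 30 and SD 12, baseline-to-12-month correlation 0.6 to 0.85, and 6,000 nulls per correlation. Keeping the best of raw, square root, log and log-ratio of means gave 6.8%, 6.7% and 7.1%. Adding a median analysis gave 8.1%, 9.1% and 9.8%.

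**Step 5: direction.** By symmetry about half of the false positives favour exercise: 6.3%/2 ≈ 3.1% to 7.1%/2 ≈ 3.5%, against 2.5%. A direct count for the four mean-based options (gamma, mean 30, SD 12; 8,000 nulls per correlation) gave 3.1% to 3.5%, against 2.3% to 2.5% for the raw scale alone.

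**The case against.** The strongest reply is that the plan, followed as written, holds its error rate. It has a default, a residual-based reason for leaving it, a bar on using the preliminary models for treatment effects, and effect estimation placed last. This stands: the residual rule gave 4.8% to 5.2%. But the bar covers the preliminary models and not the descriptive summaries that come before them. Without a numeric trigger, adherence also cannot be checked afterwards.

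Second, the ceilings assume that every candidate test is computed and the best one kept, whether or not the residuals justify leaving the default. Boxplots and densities do not show p-values on each scale, and the mean-based tests are highly correlated. This also stands. The ceilings bound the harm and do not predict it.

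Third, quantile regression is reserved for bounded integer scores with limited range or floor or ceiling effects. A score with mean 30 and SD 12 lies 30/12 = 2.5 SD above zero, so the 8% to 10% range reaches the primary outcome only if such effects are judged present.

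Fourth, the SAP already has a likelihood guide for Box-Cox, BIC for covariance, and a comparison with multinomial models under Sensitivity analyses. These help, but none commits to reporting the default if it is replaced, and the comparison does not change which test decides the claim.

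Fifth, the relevant distribution is conditional on treatment and time, so fully pooled residuals would hide arm-specific variance. This is fair, and it shapes the fix. The Overview also cites a published design paper, not available here, which may settle the primary analysis.

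**Conclusion.** The concern holds in limited form. The default can be replaced, for any outcome including the primary, by judgement made after arm-by-visit results are visible, and no trigger, masking or lock is stated. Control at 5% then depends on the analyst's discipline and not on the procedure.

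Under the assumed shapes and correlations, with 125 per arm and complete data, error is about 5% if the residual rule is followed. The ceiling is about 6% to 7% two-sided across mean-based scales, and about 8% to 10% only if median regression is admitted.

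A reader might infer that scale and model are left open for every outcome, that looking at residuals itself inflates error, or that the true error is 8% to 10%. The documents support none of these. The default gives way only on judged incompatibility, the residual rule kept its level, and the larger figures are worst cases counted in both directions. Nor does silence about masking the analyst show that any choice was or will be swayed.

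**What to change.** - Make the scale, link and model decisions on residuals centred within treatment-by-visit cells, with arm labels and cell means hidden. This keeps the saturated model that the SAP wants.
- Defer by-arm summaries, boxplots, densities and the six-cell residual-versus-predicted plots until the choice for each outcome is recorded in a dated memo.
- Always report the default raw-scale linear mixed model for MDS-UPDRS III alongside any replacement.

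The cost is one masked data set and one memo. The downside is that arm-specific variance differences are seen only after unmasking, unless variances are shown under coded arm labels. If the by-arm displays have already been seen, masking cannot be restored, and the third item is the part that still helps. Making the raw scale the sole confirmatory analysis whatever the fit is more debatable and is not needed here. This is a cheap improvement.
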